### 3.3.4 Removal of patients from therapy or assessments

#### 3.3.4.1 Removal of individual patients

An individual patient is to be withdrawn from the trial if:

- The patient / parent / legal guardian withdraws consent, without the need to justify the decision.

An individual patient is to be discontinued from trial treatment, but will remain part of the study and analysis population:

- If the patient is no longer able to take trial medication for other medical reasons (e.g. surgery, AEs, other diseases or concomitant therapies).
- If the patient is noncompliant with study drug administration despite all possible efforts.
- If, in the opinion of the Investigator, continuation on the study drug is not in the patient's best interest, if eligibility criteria are being violated, or if the patient fails to comply with the protocol (e.g. non-attendance at trial assessments).
- In the event that a recurrent thromboembolic event as assessed by appropriate imaging modalities is observed or if the patient experiences a drug-related significant or drug-related serious AE or if drug toxicity is observed.
- If the patient does not reach a total dabigatran plasma trough concentration within the pre-specified therapeutic range after one dose adjustment.
- If the patient becomes pregnant or a pregnancy is suspected during the trial the patient will be discontinued from the dabigatran treatment and will be put on an appropriate therapy per investigator judgment. The patient will be followed up until the end of the study and until the birth or otherwise termination of the pregnancy. For further information, including the process for follow up on the outcome of the pregnancy please see [Section 5.2.2.2](#).
- If a patient develops an active meningitis, encephalitis, or intracranial abscess.

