**Proprietary confidential information.**

[figure not shown]
© 2019 Boehringer Ingelheim International GmbH or one or more of its affiliated companies. All rights reserved.

This document may not - in full or in part - be passed on, reproduced, published or otherwise used without prior written permission.

dialyzable, however there is limited clinical experience in this setting. The amount of drug cleared by dialysis is proportional to the blood flow rate.

There is some experimental evidence to support the role of agents such as activated prothrombin complex concentrates (APCC, e.g. FEIBA), recombinant Factor VIIa and three or four factor concentrates (Factors II, IX and X with or without Factor VII) in reversing the anticoagulant activity of dabigatran. The usefulness in clinical settings has not yet been systematically demonstrated. Consideration should also be given to administration of platelet concentrates in cases where thrombocytopenia is present or long-acting antiplatelet drugs have been used. All symptomatic treatment has to be given according to the physician's judgment.

A summary of how to manage bleedings on dabigatran etexilate is outlined in Figure 4.2.1: 1.

 for bleeding definitions see Section 5.2.1

 when appropriate

 recommendations based on limited clinical or non-clinical data only, limited or no experience in volunteers or patients

Figure 4.2.1: 1 Management of bleeding on dabigatran therapy ([P10-03790](#))

Proprietary confidential information.

© 2019 Boehringer Ingelheim International GmbH or one or more of its affiliated companies. All rights reserved.

This document may not - in full or in part - be passed on, reproduced, published or otherwise used without prior written permission.

Dabigatran etexilate must be stopped if a major bleeding event is observed. Initiation of any other alternative therapy for secondary VTE prevention after complete haemostasis has been achieved is at the Investigator discretion.

Clinically relevant non-major bleeds or minor bleeds:

If a patient experiences a clinically relevant non-major bleed or minor bleed, dabigatran etexilate may be continued, temporarily interrupted or permanently discontinued, at the discretion of the Investigator. It is not a requirement, however, that study drug be stopped in these cases.

Management of dabigatran etexilate prior to and after planned surgery:

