### 6.2.3 End of trial and follow-up period

Follow-up Visit should be planned for 28 days after last drug intake. For the assessments and procedures to be done during the Follow-up Visit refer to the [Flow Chart](#).

All patients who prematurely discontinue treatment will be invited to perform an eEOT Visit. Subsequently they will be followed up according to the remaining visit schedule until the end of the study. At these visits collection of AEs, outcome events (e.g. occurrence of PTS, VTE, bleeding events, etc.) and use of concomitant medication will be made.

Patients that are not actively taking study drug and their parent/legal guardian may be less motivated to adhere to the study visit schedule. Investigator and site staff should work to detect early signs of losing interest and readily present such patients (not actively taking study drug) and their parent/legal guardian with the following opportunities to encourage continued participation:

- continue to attend regularly scheduled study visits until the trial ends
- conduct only the final visit in person. All other visits would be done over the phone.
- conduct all remaining study visits over the phone
- discontinue participation in remaining trial activities but permit collection of vital status and outcome events at the end of the trial.
- discontinue participation in remaining trial activities but permit collection of vital status at the end of the trial.

The patient / parent / legal guardian will be asked to choose the most rigorous follow-up they are willing to comply with.

For patients who completely withdraw consent no more data on their medical information will be requested.

The site must make periodic documented attempts (approximately every three months) to locate patients who are lost to follow up (LTFU).

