#### 7.3.1 Primary analyses

The primary analyses will be based on the primary safety endpoints. The recurrence of VTE, major bleeding events, minor (including clinically relevant non-major (CRNM)) bleeding events, overall mortality and mortality related to thromboembolic events will be analysed as time-to-event and will be summarized by Kaplan-Meier estimates. The rate of occurrence of events at 6 and 12 months will also be provided by K-M estimation. Patients who do not have any of the events or drop out early will be considered as censored for this analysis. Additionally, descriptive rate with number of patients with event divided by total treated patients will also be provided. Early drop out and lost-to-follow-up will be considered as non-event. The components of the composite event will be summarized as below:

- Recurrence of venous thromboembolism will be summarized by Kaplan-Meier estimate of time to first recurrence of VTE. The rate of recurrence at 6 and 12 months will also be provided by K-M estimation. Patients, who do not experience recurrent VTE by the time of analyses, drop out from the study, or die from non-VTE related cause will be considered as censored. The descriptive rate of number of patients with event divided by total treated patients will also be provided. Early drop out and lost-to-follow-up will be considered as non-event when calculating the descriptive rate.
- Major bleeding and minor (including clinically relevant non-major (CRNM)) bleeding will be analysed by K-M estimate of time to first occurrence as competing events. The K-M rate estimate at 6 and 12 month will be provided. The descriptive rate will also be calculated by dividing number of patients with major / minor bleeding by the number of total treated patients. Early drop out, lost-to-follow-up and non-bleeding related death will be considered as non-event and censored.

Proprietary confidential information.

© 2019 Boehringer Ingelheim International GmbH or one or more of its affiliated companies. All rights reserved.

This document may not - in full or in part - be passed on, reproduced, published or otherwise used without prior written permission.

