- Mortality overall and related to thrombotic or thromboembolic event will be summarized separately by K-M estimate of time to death. The K-M rate and descriptive rate at 6 and 12 month will be calculated. Early drop out and lost-to-follow-up will be considered as non-event. Non-thrombotic or non-thromboembolic related death will be considered as censored case for mortality due to thrombotic or thromboembolic events.

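### Section 7.3.1 calls major and minor bleeding competing events, but a minor bleed does not preclude a major one, so a later major bleed could drop out of the 6- and 12-month rate

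*Protocol*

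**What the plan says.** Major and minor (including CRNM) bleeding at 6 and 12 months is a primary endpoint (Protocol, Section 5.2.1). Section 7.3.1 describes its analysis in two places.

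- The opening paragraph lists major bleeding and minor bleeding as separate items that "will be analysed as time-to-event and will be summarized by Kaplan-Meier estimates".
- The bleeding bullet says that the two types of "bleeding will be analysed by K-M estimate of time to first occurrence as competing events", with Kaplan-Meier rates at 6 and 12 months. Its censoring rule is "Early drop out, lost-to-follow-up and non-bleeding related death will be considered as non-event and censored". It adds a crude rate, obtained by "dividing number of patients with major / minor bleeding by the number of total treated patients".

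The mortality bullet that follows is worded differently: its two outcomes "will be summarized separately by K-M estimate of time to death".

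**The concern.** A competing event is one that precludes the event of interest or ends its observation. A minor nosebleed does neither for a later major bleed. An analyst who takes the label at its word has two usual options: censor the major-bleed curve at a minor bleed, or count only the first bleed of any type. Either way, a major bleed that follows a minor one is not counted as an event. An analyst who follows the opening paragraph and the censoring list counts it. The same data can therefore give two different rates for a primary safety endpoint on which few major bleeds are expected.

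**Working it through.** **1. Does a minor bleed compete with a major one under the protocol's rules?**

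- Section 5.2.1 defines a minor bleed as an overt bleed that meets neither the major nor the CRNM criteria. Fatal bleeding is classed as major, so the patient survives a minor bleed.
- Section 4.2.1, on drug handling after a CRNM or minor bleed: "It is not a requirement, however, that study drug be stopped in these cases".
- Section 3.3.4.1, on patients taken off drug: "An individual patient is to be discontinued from trial treatment, but will remain part of the study and analysis population".
- Section 6.2.3 keeps bleeding among the outcomes collected at the remaining visits after early discontinuation.

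A major bleed after a minor one is thus possible and, under the standard follow-up, observed. No other place in the protocol gives the label a different meaning.

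**2. Is the section consistent with itself?**

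The bullet's censoring list names drop-out, loss to follow-up and non-bleeding death. It does not name a bleed of the other type. The list and the opening paragraph imply two separate curves; the label implies otherwise.

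**3. How sparse are the data?**

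The protocol's only related figures are in Section 7.6, and they reproduce. The chance of at least one event in 100 patients is 1 − 0.95^100 = 99.4% at a 5% rate and 1 − 0.99^100 = 63.4% at 1%. Section 2.3 cites major bleeding in 0.5–1.7% of anticoagulated children, which is 0.5 to 1.7 patients per 100.

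**4. Illustration of the size**

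Inputs:
- R, the overall major-bleed risk, is 1.7% or 0.5%. This is the range in Section 2.3, treated here as a 12-month risk, which the protocol does not say it is.
- m, the 12-month minor/CRNM risk, is assumed at 20% or 40%, with 10% as a low case.
- k, the ratio of the major-bleed hazard after a minor bleed to the hazard before it, is assumed at 0.5, 1 or 3.
- Hazards are constant over 12 months.

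Formulas, with time t in years and t = 1 for 12 months:
- Minor hazard λ = −ln(1 − m).
- Major bleed as first bleed: A = h/(h + λ) × (1 − exp(−(h + λ)t)), where h is the major hazard before any minor bleed.
- Major bleed after a minor one: B = ∫₀ᵗ λ exp(−(h + λ)s) × (1 − exp(−kh(t − s))) ds.
- h is solved so that A + B = R at t = 1.
- A first-bleed cumulative incidence reports A. A Kaplan-Meier curve censored at the minor bleed reports 1 − exp(−h).
- Chance that at least one of 100 patients has an omitted major bleed: 1 − (1 − B)^100.

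Worked case (R = 1.7%, m = 20%, k = 3): λ = 0.2231 and h = 0.01422, so A = 1.266% and B = 0.434%. The share omitted is 0.434/1.7 = 25.5%. The censored Kaplan-Meier rate is 1 − exp(−0.01422) = 1.41%. The chance is 1 − (1 − 0.00434)^100 = 35.3%.

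Results at 12 months for R = 1.7% (m = 20% / 40%):

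| k | First-bleed incidence A | Share omitted | Censored K-M | Chance of ≥1 omitted in 100 |
|---|---|---|---|---|
| 0.5 | 1.61 / 1.49% | 5.5 / 12.2% | 1.79 / 1.91% | 8.9 / 18.7% |
| 1 | 1.52 / 1.33% | 10.3 / 21.6% | 1.70 / 1.70% | 16.1 / 30.8% |
| 3 | 1.27 / 0.93% | 25.5 / 45.1% | 1.41 / 1.19% | 35.3 / 53.7% |

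Other settings, chance of at least one omitted for k = 0.5, 1 and 3:
- R = 0.5%, m = 20–40%: 3–6%, 5–10%, 12–20%.
- R = 1.7%, m = 10%: 4%, 8%, 21%.
- R = 1.7%, m = 20–40%, counted to 6 months (t = 0.5, same h): 2–6%, 5–10%, 11–19%.

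The first-bleed incidence is always below the true 1.70%. The censored Kaplan-Meier rate is too high if the hazard falls after a minor bleed, too low if it rises, and unbiased only if it is unchanged.

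**The case against.** The strongest reply is that the operative text already gives the right analysis. No sentence tells the analyst to stop or censor at a bleed of the other type, so the omission arises only if three words override an explicit censoring list. The label may loosely mean that any one bleed falls into a single class, and a statistical analysis plan may settle it. This lowers the likelihood of harm. It does not make the wording right: a plan that follows the label carries the error forward, and one that ignores it departs from the protocol.

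Second, fatal bleeding is a major bleed and does preclude a later minor one. That is correct, but it concerns only the minor-bleed curve. There the opening paragraph's general rule already censors a patient who dies without the event.

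Third, drug may be stopped after a minor bleed, and patients off drug may choose reduced follow-up, down to vital status only. Some later major bleeds would then go unobserved under any analysis. This qualifies the claim about observation without making a minor bleed a competing event.

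Fourth, the size rests on assumptions, and the 54% needs the worst value of each. With an unchanged hazard the censored Kaplan-Meier rate has no bias. Even the largest shift, from 1.70% to 0.93%, is small beside the intervals in Table 7.6:1 (0.18–5.45 at 1%, 0.55–7.00 at 2%). All of this stands.

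Finally, nothing is decided on this figure. Section 7.2 rules out hypothesis testing, the crude rate can count the later major bleed, and Section 7.3.3 tabulates on-treatment bleeding with the adverse events. This stands too, and it limits the weight of the point.

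**Conclusion.** The concern holds. The label is wrong under the protocol's own definitions and follow-up rules, and it conflicts with the opening paragraph and the censoring list of the same section. That conclusion needs no assumption about rates. The numerical effect does: it depends on an assumed minor-bleed risk, an assumed change in hazard after a minor bleed, and reading the cited 0.5–1.7% as a 12-month risk. Over the 20–40% minor-risk grid, the chance of losing at least one major bleed per 100 patients from the time-to-event rate runs from 3% to 54%. With so few events expected, one event more or less visibly changes the reported rate and could make the Kaplan-Meier and crude figures disagree for no clinical reason. No major bleed would go unreported. This is a modest correction to one primary summary that should be made.

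**What to change.** In the bleeding bullet of Section 7.3.1, delete the words that call the two bleed types competing events. Add one sentence: time to first major bleed and time to first minor (including CRNM) bleed are each estimated by Kaplan-Meier in the treated set, and a bleed of the other type is neither an event nor a reason for censoring. If time to first bleed of any type is also wanted, name it as an additional summary. The existing censoring rules can stay.

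The cost is one phrase removed and one sentence added. No data collection changes and standard software suffices. Compared with an analysis that followed the label, the reported rate may move slightly in either direction.

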An open-label multicentre randomized study (the REVIVE study) comparing the efficacy and safety of a low molecular weight heparin (reviparin-sodium) to UFH/VKA for the treatment of VTE in children, showed that at 3 months post-therapy, 2/36 patients (5.6%) treated with reviparin-sodium had recurrent VTE or death compared to 4/40 patients (10.0%) receiving UFH/VKA (odds ratio = 0.53; 95% CI=(0.05, 4.00); Fisher's exact test: 2P= 0.677). There were 7 major bleeds reported, 2/36 (5.6%) in the reviparin-sodium group and 5/40 (12.5%) in UFH/VKA group (odds ratio = 0.41; 95% confidence interval 0.04, 2.76); Fisher's exact test: P=0.435). There were 5 deaths reported during the study period, 1 (2.8%) in the reviparin-sodium group and 4 (10.0%) in the UFH/VKA group. All five deaths were considered unrelated to VTE but one was due to an intracranial haemorrhage in the UFH/VKA group. Due to challenges with patient recruitment, REVIVE was closed prematurely. The REVIVE study provides valuable information on the incidence of recurrent VTE, major bleeding and problematic issues associated with therapy of VTE in children ([R06-2304](#)).

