### 7.2 NULL AND ALTERNATIVE HYPOTHESES

There is no hypothesis testing for this trial.

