### 7.3.2 Secondary analyses

Secondary analyses are planned for occurrence of post-thrombotic syndrome (PTS), number of dabigatran etexilate dose adjustments (i.e. Number of patients with dabigatran dose adjustments) and pharmacodynamic assessments at Visit 3 (after at least six consecutive dabigatran etexilate doses) and after at least 3 days following any dabigatran etexilate dose adjustment.

- Occurrence of PTS will be summarized by K-M estimate of time to first occurrence. The K-M rate and descriptive rate at 6 and 12 month will be calculated. Early drop out, lost-to-follow-up and death will be considered as non-event and censored.
- Frequency of dabigatran etexilate dose adjustments will be summarized descriptively. This refers to the number of patients with dabigatran etexilate dose adjustment during treatment period because each patient is allowed to have only one dose adjustment.
- pharmacodynamic analyses details can be found in [Section 7.3.5](#) and [7.3.6](#).

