#### 7.6 DETERMINATION OF SAMPLE SIZE

The design of this study (including the definition of endpoints and sample size) has been agreed with the European Medicines Agency's Paediatric Committee. A minimum of 100 patients will be entered in this trial, including patients rolling over from study 1160.106, who require secondary VTE prevention and new patients who should have completed treatment for an acute VTE episode. The Data Monitoring Committee (DMC) or Sponsor may decide to keep recruitment open after 100 patients have been recruited, in case additional safety data needs to be generated.

Under the assumption of 5% of event rate for the composite of recurrent VTE, major bleeds and mortality related to thromboembolic event at 12 months, 100 patients will provide more than 99% of probability observing at least 1 event, it will provide higher than 63% of probability if the event rate is 1%. The expected 95% Wilson confidence interval for event rates under the assumption of 100 patients are provided in Table 7.6: 1.

Table 7.6:1 Expected 95% Wilson confidence interval based on 100 available patients

Observed rate (%)	95% Wilson CI
1	(0.18 – 5.45)
2	(0.55 – 7.00)
3	(1.03 – 8.45)
4	(1.57 – 9.89)
5	(2.15 – 11.2)
10	(5.52 – 17.4)
20	(13.3 – 28.9)

The sample size is considered adequate to capture any safety signal for the primary safety endpoints defined in the study.

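### Kaplan-Meier rates that censor competing deaths can slightly overstate the 6- and 12-month risks of recurrent VTE, bleeding, thrombotic death and PTS

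*Protocol*

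**What the plan says.** Section 7.3.1 (Primary analyses) makes Kaplan-Meier the estimator and fixes the time points: "The rate of occurrence of events at 6 and 12 months will also be provided by K-M estimation". It then sets a censoring rule for each endpoint.

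- **Recurrent VTE:** patients who "die from non-VTE related cause will be considered as censored".
- **Bleeding:** deaths not related to bleeding are non-events and censored. The same bullet says major and minor bleeding are analysed as competing with each other, but still by a Kaplan-Meier estimate of time to first occurrence.
- **Thrombotic mortality:** "Non-thrombotic or non-thromboembolic related death will be considered as censored case for mortality due to thrombotic or thromboembolic events".

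Section 7.3.2 (Secondary analyses) treats PTS in the same way, but for every death and not only deaths from other causes: "Early drop out, lost-to-follow-up and death will be considered as non-event and censored".

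Next to each Kaplan-Meier rate the protocol plans a descriptive rate. Section 7.3.1 defines it as patients with the event over all treated patients, with drop-outs and losses to follow-up counted as non-events. Overall mortality has its own Kaplan-Meier summary. No cumulative incidence function is named. Section 7.2 states "There is no hypothesis testing for this trial".

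**The concern.** Censoring assumes that the censored patient could still have the event later, at the same rate as those still observed. A child who has died cannot have a recurrence, a bleed, PTS or a thrombotic death. When such deaths are censored, one minus Kaplan-Meier estimates the risk in a hypothetical setting without those deaths. It does not estimate the proportion of children who actually have the event.

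The bleeding text adds an inconsistency of its own. It recognises competing events, yet names an estimator that does not give incidence under competing events, and it leaves death out of the competing set.

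The stake is how the headline numbers are read. With one arm and no test, the absolute 6- and 12-month rates are the product of the trial, and there is no between-arm contrast in which the bias might partly cancel.

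**Working it through.** **Inputs from the protocol.** Section 7.6: "A minimum of 100 patients will be entered in this trial", so n = 100. The same section gives the 5% used as the benchmark risk: "Under the assumption of 5% of event rate for the composite of recurrent VTE, major bleeds and mortality related to thromboembolic event". That 5% belongs to a composite; it is applied here to a single endpoint for illustration.

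**Input that must be assumed.** The protocol gives no expected competing mortality for this trial. The range used is 1% to 20% at 12 months.

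**The plan's own figures.** The probability of at least one event in 100 patients is 1 − 0.95^100 = 99.41% at a 5% rate and 1 − 0.99^100 = 63.40% at a 1% rate. Both agree with Section 7.6. The 95% Wilson interval for 5 of 100 is 2.15% to 11.18%, which agrees with the printed 2.15 to 11.2.

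**Size under constant hazards.** Let l = −ln(1 − K), with K the 12-month Kaplan-Meier risk, and m = −ln(1 − d), with d the 12-month competing mortality. Kaplan-Meier with deaths censored targets K. The actual cumulative incidence is

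CIF = l/(l + m) × [1 − (1 − K)(1 − d)].

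For K = 5% and d = 5% the two hazards are equal, so CIF = 0.5 × (1 − 0.95 × 0.95) = 0.5 × 0.0975 = 4.88%. For d = 10%, l = 0.0513 and m = 0.1054, so CIF = 0.3274 × (1 − 0.95 × 0.90) = 0.3274 × 0.145 = 4.75%.

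| Competing mortality (assumed) | K-M risk | Cumulative incidence | Excess, points | Excess, relative |
|---|---|---|---|---|
| 1% | 5.00% | 4.98% | 0.02 | 0.5% |
| 5% | 5.00% | 4.88% | 0.12 | 2.6% |
| 10% | 5.00% | 4.75% | 0.25 | 5.3% |
| 20% | 5.00% | 4.49% | 0.51 | 11.5% |

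The relative excess is roughly half the competing mortality and hardly depends on the event risk, so the absolute excess grows with that risk. If the Kaplan-Meier value were 21%, the PTS proportion in the Canadian registry cited in Section 1.1, the cumulative incidence would be 20.5% at 5% competing mortality and 20.0% at 10%.

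**Finite-sample check without the hazard assumption.** Take 100 patients, 5 events, 5 competing deaths and no other censoring. The actual incidence is 5/100 = 5.00%.

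- All deaths after the events: Kaplan-Meier gives 1 − 95/100 = 5.00%, so there is no bias.
- Random order: 5.13% on average.
- All deaths before the events: 1 − 90/95 = 5.26%.

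With 10 deaths, random order averages 5.27%, and the most extreme order gives 1 − 85/90 = 5.56%.

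**Part not sized.** If bleeding is analysed by type of first bleed, a first minor bleed competes with a first major bleed, and the reverse. The protocol gives no minor-bleeding rate, so no figure is put on this.

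**The case against.** **The descriptive rate is already planned.** It keeps deaths in the denominator, so they do not inflate it, and a reader will see it beside the Kaplan-Meier rate. That stands in part. The descriptive rate counts drop-outs and losses to follow-up as non-events, which pulls it down. One planned figure mishandles death and the other mishandles loss to follow-up; neither handles both.

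**It is a choice of estimand.** The risk with other deaths removed is a recognised quantity, and the rule is stated openly. But the protocol presents these figures as rates of occurrence at 6 and 12 months in a descriptive safety cohort, and its bleeding text itself speaks of competing events. Actual incidence is the natural reading.

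**The PTS rule was deliberate.** The record of Global Amendment 05 in Section 11 says that PTS cannot itself cause death. That justifies not counting deaths as PTS events. It does not justify treating them as non-informative censoring.

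**The effect is negligible and errs on the cautious side.** This largely stands. An excess of 0.02 to 0.25 points is small against an interval of 2.15% to 11.2%, no test depends on it, and overstating harm is the safer error.

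**Stronger readings that the protocol does not support.**

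- A reader might annualise the mortality in the randomised paediatric trial of LMWH against UFH/VKA described in Section 1.1. It had 5 deaths among 76 patients (6.6%), and "All five deaths were considered unrelated to VTE". Compounded over four quarters, 1 − (1 − 5/76)^4 is about 24%, which would imply an overstatement of about 14%. But the protocol places the deaths only within that trial's study period and gives no duration for them. That trial concerned initial treatment, whereas patients here have completed at least 3 months of treatment or the 1160.106 treatment period. One of the five deaths was an intracranial haemorrhage, which under Section 5.2.1 is a major bleed and so an event for bleeding, not a competing death.
- A reader might add that thrombotic and non-thrombotic mortality curves would not sum to overall mortality. No non-thrombotic mortality curve is planned.

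**Conclusion.** The point holds as a minor one. Sections 7.3.1 and 7.3.2 fix an estimator that cannot fall below the actual cumulative incidence and exceeds it once a competing death precedes a later event. It would be wrong to infer that the reported rates will certainly be too high: with no such death the bias is zero.

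For a 5% risk and competing mortality of 1% to 10%, the overstatement is about 0.5% to 5.3% relative. This rests on constant hazards, on using the composite's 5% for a single endpoint, and on an assumed mortality range. With 10 deaths and 5 events in 100 patients, the most extreme ordering gives 0.56 points. Overall mortality and the sample-size reasoning in Section 7.6 are not affected.

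**What to change.** Amend Sections 7.3.1 and 7.3.2 to replace one minus Kaplan-Meier with the Aalen-Johansen cumulative incidence at 6 and 12 months for four endpoints, with these competing events:

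- recurrent VTE: non-VTE death;
- bleeding: non-bleeding death and, where the analysis is by type of first bleed, the other bleeding type as well;
- thrombotic mortality: non-thrombotic death;
- PTS: any death.

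Continue to censor drop-outs and losses to follow-up. Keep Kaplan-Meier for overall mortality, and keep the descriptive rate as a companion figure. In the bleeding bullet, remove the pairing of Kaplan-Meier with competing events.

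The cost is a wording change and standard software. Deaths are already collected and, as part of the primary endpoints, centrally adjudicated (Section 5.2.1). No new visits, data or patients are needed.
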